## LYM 155 Summary of Changes

AMENDMENT NUMBER: 3.0

AMENDMENT DATE: 29 September 2023

---

Additions are noted by **bolding**. Deletions are noted by ~~cross outs~~.

**[contact]**

**[contact]**

### **Synopsis**

Define the conversion rate from minimal residual disease positive (MRD+) to MRD negative (MRD-) during therapy **for up to 2 years post-BMT**

Beginning at Day +100 ( $\pm 7$  days) post-BMT, subjects will receive **129+00** mg acalabrutinib twice daily (BID) until they reach 2 years post-BMT.

Acalabrutinib **129+00** mg will be self-administered orally BID for up to 2 years (**approximately 22 cycles**) on a 28-day cycle (**approximately 22 cycles**).

### **Synopsis and Section 3.2**

5. Willing and able to participate in all required evaluations and procedures in this study protocol including swallowing **tablets**~~or capsules~~ without difficulty.

### Synopsis and Section 3.3

14. Requires treatment with proton pump inhibitors (e.g., omeprazole, esomeprazole, lansoprazole, dexlansoprazole, rabeprazole, or pantoprazole). Subjects receiving proton pump inhibitors who switch to histamine 2 receptor antagonists or antacids are eligible for enrollment to this study.
20. The inability to swallow ~~tablets~~ capsules.

### Section 1.4.2

~~Acalabrutinib absorption may be lower in individuals being treated with proton pump inhibitors, histamine 2 (H2) receptor antagonists, or antacids.~~

### Section 1.6

In this study, we propose the use of acalabrutinib **129400** mg PO BID as maintenance therapy post-BMT to prolong PFS.

### Section 5

Subjects will self-administer **129400** mg acalabrutinib BID until they reach 2 years post-BMT (approximately 22 cycles).

#### Figure 1

Subjects will self-administer acalabrutinib **129400** mg BID on a 28-day cycle.

### Section 5.1

Acalabrutinib **129400** mg will be self-administered orally BID on a 28-day schedule, with or without food, until the patient has reached approximately 2 years post-BMT.

### Section 5.3

~~The effect of agents that reduce gastric acidity (i.e., proton pump inhibitors, or antacids) on acalabrutinib absorption was evaluated in a healthy volunteer study (ACE HV 004). Results from this study indicate that subjects should avoid the use of calcium carbonate containing drugs or supplements for a period of at least 2 hours before and after taking acalabrutinib. Use of omeprazole, esomeprazole, lansoprazole or any other proton pump inhibitors while taking acalabrutinib is not recommended due to a potential decrease in study drug exposure. However, the decision to treat with proton pump inhibitors during the study is at the Investigator's discretion, with an understanding of the potential benefit to the subject's gastrointestinal condition and a potential risk of decreased exposure to acalabrutinib.~~

~~Although the effect of H2 receptor antagonists (e.g. famotidine or ranitidine) on acalabrutinib absorption has not been evaluated, if treatment with an H2 receptor antagonist is required, the H2 receptor antagonist should be taken approximately 2 hours after an acalabrutinib dose.~~

### Section 6.3

- Complete blood count (CBC), and clinical chemistry panel, and coagulation testing

### Section 6.4.1, Section 6.4.2, Section 6.4.3, and Section 6.4.4

- Treatment with acalabrutinib **129400** mg PO BID

## **Section 6.5.5**

**Coagulation testing will include PT/INR or aPTT.**

## **Section 7**

### **7.1 Acalabrutinib**

| Investigational Product | Dosage Form and Strength                            | Manufacturer  |
|-------------------------|---|---------------|
| Acalabrutinib           | 129 <del>100</del> mg tablet <del>se</del> capsules | Acerta Pharma |

### **7.2 Acalabrutinib Treatment Duration**

Acalabrutinib ~~tablets~~~~capsules~~ will be self-administered BID approximately every 12 hours. The ~~tablets~~~~capsules~~ should be swallowed intact with approximately 1 cup of water. **Patients should not chew the tablets and should try to swallow tablets whole. Patients should not attempt to open capsules or dissolve them in water.**

If a dose is missed, it can be taken up to 3 hours after the scheduled time with a return to the normal schedule with the next dose. If it has been >3 hours, the dose should not be taken and the patient should take the next dose at the scheduled time. The missed dose will not be made up and must be returned to the site at the next scheduled visit.

~~Guidance on co-administration of acalabrutinib with agents that affect gastric pH is provided in Section 5.3.~~

#### **7.2.1 Labeling, Packaging, and Supply of Acalabrutinib**

**The investigational product, acalabrutinib maleate tablet, is supplied as an orange film-coated tablet containing 129 mg of acalabrutinib maleate (equivalent to 100 mg of acalabrutinib) drug substance.**

**Each tablet also contains the following compendial inactive ingredients: mannitol, microcrystalline cellulose, low-substituted hydroxypropyl cellulose, and sodium stearyl fumarate. The tablet coating contains hypromellose, copovidone, titanium dioxide, polyethylene glycol, caprylic/capric triglyceride, yellow iron oxide, and red iron oxide. Acalabrutinib is supplied as yellow and blue, opaque hard gelatin capsules filled with 100 mg of active ingredient. Each capsule also contains compendial inactive ingredients: silicified microcrystalline cellulose (which is composed of microcrystalline cellulose and colloidal silicon dioxide), partially pregelatinized starch, sodium starch glycolate, and magnesium stearate. The capsule shell contains gelatin, titanium dioxide, yellow iron oxide and indigotine (FD&C Blue 2).**

~~Acalabrutinib will be provided in white, high-density polyethylene bottles. The recommended storage condition for acalabrutinib capsules is below 30°C (86°F). Acalabrutinib maleate tablets are packed in white, high-density polyethylene (HDPE) bottles containing a silica gel desiccant and should be stored according to the storage conditions as indicated on the label. The recommended storage condition for acalabrutinib maleate tablets is below 30°C (86°F).~~

## **Section 7.4**

The subject will be instructed to bring the diary and any remaining ~~tablets~~capsules to the clinic at his/her next visit. The study staff will review the diary and ask the subject if all the ~~tablets~~capsules were administered. Any remaining or returned ~~tablets~~capsules will be counted and documented. Returned ~~tablets~~capsules must not be redispensed to another subject.

**Table 1 Acalabrutinib Dose Reduction Options**

| Starting Dose        | 1 st Dose Reduction | 2 nd Dose Reduction |
|----------------------|--------------------------------|--------------------------------|
| 129100 mg BID | 129100 mg QD            | discontinue                    |

## **Section 8.1**

The maximum dose of acalabrutinib is **129100 mg BID**.

## **Section 8.2**

If the acalabrutinib dose should be reduced and the subject is receiving acalabrutinib **129100 mg QD**, acalabrutinib should be discontinued.

## **Appendix D: Schedule of Assessments**

### **Coagulation testingu**

**129100 mg** twice daily continuously for 2 years post-BMT (~22 cycles).

### **Appendix D: Schedule of Assessments footnote u**

**u Coagulation testing will include PT/INR or aPTT.**

## LYM 155 PROTOCOL SYNOPSIS

|   |   |                           |
|---|---|---------------------------|
| Title of Study:  | Single Arm, Phase II Study of Acalabrutinib as Post-Autologous Blood or Marrow Transplant (BMT) Maintenance Therapy in Subjects with Mantle Cell Lymphoma   |                           |
| Innovations Study Number:                                  | LYM 155   |                           |
| Sponsor:   | Sarah Cannon Development Innovations, LLC   |                           |
| Study Duration:  | The total duration of the study is planned to be approximately 7 years (2 years for recruitment).   | Phase of Study: II |
| Number of Study Centers:                                   | This study will be conducted at approximately 10 sites in the United States.  |                           |
| Number of Patients:  | Approximately 50 patients are planned to be enrolled in this study.   |                           |
| Objectives:  | 
Primary Objective
 The primary objective of this study is to:
 
 
Determine the progression-free survival (PFS) rate of subjects who received at least one dose of acalabrutinib and are alive and free of disease progression or relapse at 2 years post-blood or marrow transplant (BMT).
 
 
Secondary Objectives
 The secondary objectives of this study are to:
 
 
Define the conversion rate from minimal residual disease positive (MRD+) to MRD negative (MRD) during therapy for up to 2 years post-BMT
 
Assess how MRD correlates with PFS
 
Assess the incidence of adverse events (AEs)
 
 
Exploratory Objectives
 The exploratory objectives of this study are to:
 
 
Determine how mutations correlate with disease relapse using next-generation sequencing
 
Determine the MRD correlation of bone marrow compared to blood
 
 |                           |
| Study Design:  | This is a single arm, multi-center, Phase II study of subjects with mantle cell lymphoma (MCL) who will receive acalabrutinib as maintenance therapy post-BMT. The BMT is not considered part of this study. Beginning at Day +100 ( $\pm 7$ days) post-BMT, subjects will receive 129 mg acalabrutinib twice daily (BID) until they reach 2 years post-BMT. All subjects will be followed for up to 5 years post-BMT for progression-free survival.  |                           |
| Study Drug, Dose, and Mode of Administration:              | Acalabrutinib 129 mg will be self-administered orally BID for up to 2 years (approximately 22 cycles) on a 28-day cycle. Acalabrutinib will be self-administered until disease progression, unacceptable toxicity, or the subject discontinues treatment for any other reason.  |                           |
| Inclusion Criteria for Initial Enrollment (Screening #1) : | 
 
Written informed consent according to local guidelines, signed by the subject or by a legal guardian prior to the performance of any study-related procedures.
 
Men and women <math>\geq 18</math> years-of-age.
 
A diagnosis of MCL confirmed by one of the following: 
 
- t(11;14) detected by fluorescence in situ hybridization (FISH), conventional cytogenetics, or other molecular evaluation
 
- expression of cyclin D1 confirmed by immunohistochemistry
 
 
 
Subject must have completed induction chemotherapy and plan to and be eligible to receive their first BMT per standard of care
 
Availability of an archival paraffin-embedded tumor block for MRD testing
 
   |                           |

|  |  |
|--|--|
|  | 
 
6. The Investigator anticipates that the subject will meet the appropriate lab requirements listed in Screening #2 by Day 100
 
7. Patients who received prior therapy with a Bruton's tyrosine kinase (BTK) inhibitor are eligible to enroll.
 
  |
| Inclusion Criteria after BMT, Prior to Day 100 (Screening #2) | 
 
1. Adequate organ system functions defined as: 
 
- Absolute neutrophil count <math>\geq 1,000/\text{mm}^3</math>.
 
- Platelet count <math>\geq 75,000/\text{mm}^3</math>. Platelet infusions to meet eligibility criteria are not allowed within 3 days of study enrollment.
 
- Calculated creatinine clearance (CrCl) <math>\geq 30 \text{ mL/min}</math> as calculated by the Cockcroft-Gault method.
 
 
 
 
Estimated CrCl (glomerular filtration rate) = <math>(140 - \text{age [years]}) \times (\text{weight [kg]}) \times F^a</math>
 <math>(72 \times \text{serum creatinine [mg/dL]})</math>
 
a where F = 0.85 for females and F = 1 for males
 
 
- Total bilirubin <math>\leq 1.5 \times</math> the upper limit of normal (ULN) (except for previously documented Gilbert's syndrome)
 
- Alanine aminotransferase/aspartate aminotransferase <math>\leq 2.5 \times</math> ULN
 
 
 
2. Eastern Cooperative Oncology Group (ECOG) performance status of 0, 1, or 2
 
3. Subjects who did not receive an anti-cancer therapy (including surgery, radiotherapy, chemotherapy, immunotherapy, or investigational therapy) during the time between their transplant and the start of study therapy. Subjects must have recovered (e.g. Grade <math>\leq 1</math> or baseline) from AEs associated with prior cancer therapy. Note: Subjects with Grade <math>\leq 2</math> neuropathy or Grade <math>\leq 2</math> alopecia are an exception to the latter criterion and may qualify for the study.
 
4. Women of childbearing potential (WoCBP) who are sexually active with male partners must use highly effective methods of contraception during treatment and for 2 days after the last dose of acalabrutinib. For male subjects with a pregnant or non-pregnant WoCBP partner, no contraception measures are required. A WoCBP must have a negative pregnancy test (urine or serum) at the time of screening and 72 hours before starting the study drug or have evidence of non-childbearing potential by fulfilling one of the following criteria: 
 
- Post-menopausal women, defined as either women aged <math>>50</math> years and amenorrheic for <math>\geq 12</math> months following cessation of all exogenous hormonal treatments or women <math><50</math> years old who have been amenorrheic for <math>\geq 12</math> months following the cessation of exogenous hormonal treatments, and have serum follicle-stimulating hormone (FSH) and luteinizing hormone (LH) levels in the post-menopausal range for the institution.
 
- Documentation of irreversible surgical sterilization by hysterectomy, bilateral oophorectomy or bilateral salpingectomy, but not tubal ligation.
 
- Medically confirmed, irreversible premature ovarian failure.
 
 
 
5. Willing and able to participate in all required evaluations and procedures in this study protocol including swallowing tablets without difficulty.
 
6. Ability to understand the purpose and risks of the study and provide signed and dated informed consent and authorization to use protected health information.
 
 |

|                             |  |
|-----------------------------|--|
| Exclusion Criteria : | 
 
1. Subjects who have relapsed or progressed at any time prior to BMT
 
2. Subjects with known mutations that confer resistance to a BTK inhibitor.
 
3. Confirmed clinical disease progression since the time of BMT
 
4. Prior malignancy (or any other malignancy requiring active treatment), except for adequately treated basal cell or squamous cell skin cancer, in situ cervical cancer, or other cancer from which the subject has been disease free for <math>\geq 2</math> years or that will not limit survival to <math><2</math> years. The exceptions are: 
 
– Subjects treated with curative intent <math><2</math> years prior to enrollment and have a low probability of recurrence.
 
 
 
5. Clinically significant cardiovascular disease such as uncontrolled or symptomatic arrhythmias, congestive heart failure, or myocardial infarction within 6 months of screening, or any Class 3 or 4 cardiac disease as defined by the New York Heart Association Functional Classification (Appendix B).
 
6. Malabsorption syndrome, disease significantly affecting gastrointestinal function, resection of the stomach or small bowel that is likely to affect absorption, symptomatic inflammatory bowel disease, partial or complete bowel obstruction, or gastric restrictions and bariatric surgery, such as gastric bypass.
 
7. Known history of infection with human immunodeficiency virus (HIV) or any uncontrolled active systemic bacterial, fungal, parasitic or viral infection. Infections are considered controlled if appropriate therapy has been instituted and, at the time of screening, no signs of infection progression are present.
 
8. Known history of drug-specific hypersensitivity or anaphylaxis to study drug (including active product or excipient components).
 
9. Active bleeding or history of bleeding diathesis (e.g., hemophilia or von Willebrand disease).
 
10. Uncontrolled autoimmune hemolytic anemia or idiopathic thrombocytopenic purpura.
 
11. Requires treatment with a strong cytochrome P450 3A4 (CYP3A4) inhibitor/inducer (see Appendix G).
 
12. Requires or is receiving anticoagulation treatment with warfarin or equivalent vitamin K antagonists (e.g., phenprocoumon) within 7 days of first dose of study drug.
 
13. Prothrombin time (PT)/international normalized ratio (INR) or activated partial thromboplastin time (aPTT) <math>>2 \times</math> ULN (in the absence of lupus anticoagulant).
 
14. History of significant cerebrovascular disease/event, including stroke or intracranial hemorrhage, within 6 months before the first dose of study drug.
 
15. Major surgical procedure within 28 days of first dose of study drug. Note: If a subject had major surgery, they must have recovered adequately from any toxicity and/or complications from the intervention before the first dose of study drug.
 
16. Hepatitis B or C serologic status: subjects who are hepatitis B core antibody (anti-HBc) positive and who are hepatitis B surface antigen (HbsAg) negative will need to have a negative polymerase chain reaction (PCR) result. Those who are HbsAg positive or hepatitis B PCR positive will be excluded. Subjects who are hepatitis C antibody positive will need to have a negative PCR result. Those who are hepatitis C PCR positive will be excluded.
 
 |
|-----------------------------|--|

|                                 |   |
|---------------------------------|---|
|                                 | 
17. Breastfeeding or pregnant.
 
18. Concurrent participation in another therapeutic clinical trial.
 
19. Psychological, familial, sociological, or geographical conditions that do not permit compliance with the protocol.
 
20. The inability to swallow tablets.
   |
| Statistical Methodology: | 
The primary endpoint is the percentage of subjects who are alive and free of disease progression or relapse at 2-years post-BMT. A sample size of 45 subjects produces a two-sided 95% confidence interval of 65%-95% when the observed percentage is 80%. To account for a 10% non-evaluable rate, the total sample size will be 50 patients.
 |

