### **10.2 Sample Size Considerations**

The primary endpoint is the percentage of patients who are alive and free of PD or relapse at 2 years post-BMT. A sample size of 45 patients produces a two-sided 95% CI of 65%-90% when the observed percentage is 80%. To account for a 10% non-evaluable rate, the total sample size will be 50 patients.

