### **10.4 Data Analysis**

Descriptive statistics, including mean, median, standard deviation, and range for all continuous measures, will be tabulated and reported. Percentages and frequencies for all categorical measures will also be presented. Time-to-event endpoints will be reported using Kaplan-Meier estimates, with 95% CIs for median time to event. A full description of the analysis will be included in the Statistical Analysis Plan.

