#### **10.4.2 Efficacy Analysis**

All efficacy analyses will be performed using the Efficacy Analysis Set.

- PFS is defined as the time from Day 0 of BMT to objective radiological PD or death on study. PFS will be evaluated as Kaplan-Meier estimates of the percentage of subjects who receive at least one dose of study drug and who are alive and free of PD or relapse at 2 years post-BMT according to RECIL (Younes et al 2017). Data for subjects who are still alive and free from progression at the time of data cut-off date, are lost to follow-up, have discontinued the study, or have initiated a subsequent protocol therapy will be censored on last assessment (or, if no post-baseline tumor assessment, at the time of first dose plus 1 day). Approximate 95% CI for median duration of PFS will be computed using the formula proposed by Brookmeyer and Crowley.
- Minimal residual disease status will be examined by NGS on all bone marrow aspirate and blood samples collected up to 2 years post-BMT to determine the conversion rate from MRD+ to MRD while taking acalabrutinib, correlate MRD status with PFS, and identify mutations that correlate with disease relapse. An MRD status will be defined as all results from whole blood and BM that are negative for the presence of residual clonal cells (with assay sensitivity of 10^-6). An MRD+ status will be defined as all results from whole blood or BM that are positive for residual clonal cells per Adaptive Biotechnologies' reporting methods.

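### The synopsis gives 65%-95% as the planning 95% confidence interval for the 2-year rate; Section 10.2 gives 65%-90% from the same inputs, and the synopsis upper limit cannot be reproduced

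*Combined protocol and SAP*

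**What the plan says.** The synopsis, under Statistical Methodology, states: "A sample size of 45 subjects produces a two-sided 95% confidence interval of 65%-95% when the observed percentage is 80" per cent.

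Section 10.2 (Sample Size Considerations) states: "A sample size of 45 patients produces a two-sided 95% CI of 65%-90% when the observed percentage is 80" per cent.

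Both places define the primary endpoint as the percentage alive and free of progression or relapse at 2 years post-BMT. Both then allow for non-evaluable patients in the same way; in Section 10.2 this reads: "To account for a 10% non-evaluable rate, the total sample size will be 50 patients". Neither place names the method used for the interval. The Amendment 3.0 summary of changes, as supplied, does not touch this sentence, so the conflict lies between two current parts of the protocol.

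**The concern.** The endpoint, number of patients, observed rate, confidence level and sidedness are identical in the two places, yet the upper limits are 95% and 90%. One set of inputs and one method cannot produce both.

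The point deserves correction because Section 10 gives no null rate, power or success threshold for the primary endpoint. The width of this interval is the only argument offered for 45 evaluable and 50 total patients. A reader comparing synopsis and body finds two statements of the planned precision and must recompute to learn which is right. Text copied from the synopsis would carry the wrong figure forward.

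**Working it through.** **Inputs**
- n = 45, observed 80%, two-sided 95% level: synopsis and Section 10.2.
- 80% of 45 is exactly 36, so x = 36 and p = 0.80.
- Non-evaluable rate 10%, total 50: both places.

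**Step 1. Reproduce the Section 10.2 figure.** The exact (Clopper-Pearson) limits are beta quantiles:
- lower = 2.5% quantile of Beta(x, n - x + 1) = Beta(36, 10) = 0.654
- upper = 97.5% quantile of Beta(x + 1, n - x) = Beta(37, 9) = 0.904

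The result, 65.4%-90.4%, rounds to 65%-90%. Section 10.2 is reproduced.

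**Step 2. Look for any 95% method that gives the synopsis figure.** For example, the Wald interval is p ± 1.96 × √(p(1 - p)/n) = 0.80 ± 1.96 × √(0.16/45) = 0.80 ± 0.117, or 68.3%-91.7%. A continuity correction of 1/(2n) = 0.011 widens this to 67.2%-92.8%. All ten methods for 36/45:

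| Method (two-sided 95%) | Lower % | Upper % |
|---|---|---|
| Clopper-Pearson | 65.4 | 90.4 |
| Wilson | 66.2 | 89.1 |
| Wilson, continuity-corrected | 64.9 | 89.9 |
| Agresti-Coull | 66.0 | 89.3 |
| Jeffreys | 66.7 | 89.6 |
| Logit | 65.8 | 89.3 |
| Wald | 68.3 | 91.7 |
| Wald, continuity-corrected | 67.2 | 92.8 |
| Greenwood, log scale | 69.1 | 92.6 |
| Greenwood, log-log scale | 65.1 | 89.1 |

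The two Greenwood rows assume no censoring before 2 years. The highest upper limit is 92.8%, so none reaches 95%. Two methods, Clopper-Pearson and the continuity-corrected Wilson interval, round to 65%-90%.

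**Step 3. Try other explanations of 65%-95%.**
- Full enrolment: 40/50 gives an exact interval of 66.3%-90.0%.
- A higher observed rate: an exact upper limit near 95% with n = 45 needs 39/45 (86.7%), for which the interval is 73.2%-94.9%. The lower limit is then no longer 65%.
- A smaller n: 65%-95% is 80% ± 15 points. Setting 1.96 × √(0.16/n) = 0.15 gives n = 1.96² × 0.16/0.15² ≈ 27, not 45.
- A different level: a 99% Wald interval for 36/45 is 64.6%-95.4%, but the text says 95%.

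**Step 4. Size of the discrepancy.** The upper limit differs from the exact value by 95 - 90.4 = 4.6 points. The stated width is 95 - 65 = 30 points, against 90.4 - 65.4 = 25.0.

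**Step 5. Check the enrolment figure.** 45/(1 - 0.10) = 50, as both places state.

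**The case against.** There is no good defence of the 95% figure itself; the case on the other side concerns how firmly to state the point and how much weight it deserves.

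First, no method is named, so reading Section 10.2 as an exact interval is an inference. Section 10.4.2 also plans a Kaplan-Meier estimate with censoring, not a simple proportion. This stands as a caution on wording. It does not rescue the synopsis, because the planning statement is given as a number of patients and an observed percentage, and no 95% method tried on those inputs reaches 95%.

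Second, the source of the slip is unknown. It could be a typing error, a symmetric ±15 points, or an interval at the wrong level. That is so, and no explanation is claimed here.

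Third, the practical consequence is close to nil. The full statistical section carries the reproducible figure, the lower limits agree, and the study-wide stopping rule in Section 3.5 concerns adverse events. The error also makes planned precision look worse than it is, so it does not flatter the design. All of this stands, and it is why the point is minor.

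**Conclusion.** The point holds, as a minor error. The synopsis upper limit of 95% is wrong for its own inputs. It should be about 90%, which makes it about 5 points too high and the stated width 30 points instead of 25. The conclusion rests on reading 80% of 45 as 36 patients and on the stated two-sided 95% level; it does not depend on which of the ten interval methods the sponsor used. That 65%-90% is the intended figure is inferred from its agreement with the exact interval and its presence in Section 10.2. The planned 45 evaluable and 50 total patients, the lower limit and the analysis are unaffected.

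**What to change.** In the synopsis, under Statistical Methodology, change the interval from 65%-95% to 65%-90% so that it matches Section 10.2. This is one figure; it needs no patients, no data and no change to the sample size.

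Optionally, and not as part of the error, Section 10.4.2 could name the 95% interval method for the 2-year Kaplan-Meier rate, since the interval method named there is for the median: "Approximate 95% CI for median duration of PFS will be computed using the formula proposed by Brookmeyer and Crowley". Section 10.4 leaves the full description to the Statistical Analysis Plan, which was not available for this check. If that plan already names a method, a cross-reference is enough.
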